## Justification of FAS and mFAS Sample Size

The planned sample size was expected to provide adequate power for the comparisons between fasinumab doses and naproxen at week 16 for the WOMAC pain and physical function scores and the PGA score and provide long term data for safety assessment.

The sample size for the full analysis set (FAS) population was based on results of the WOMAC pain and physical function subscale scores and the PGA from the R475-PN-1227 study. The calculation of sample size assumed a 2-sided alpha level of 0.025 and a 15% dropout rate up to week 16 and a 30% dropout rate up to week 52. Enrollment of 840 patients in the fasinumab 1 mg Q4W group and 280 patients in the placebo group would have provided at least 99% power to detect an effect size of 0.46 in the WOMAC pain and physical function subscale scores at week 16 and week 52. This sample size would have provided 99% power to detect an effect size of 0.36 in PGA for an absolute treatment difference of 0.4 with a standard deviation (SD) of 1.1 at week 16, and 98% power at week 52 for the FAS.

For the fasinumab 1 mg Q8W group, the 600 patients in the FAS population were to be compared to approximately 200 patients in the placebo group who were enrolled under amendment 5 global. For such comparisons, a 2-sided alpha level of 0.025 and a 15% dropout rate up to week 16, and a 30% dropout rate up to week 52, were assumed. Additionally, the effect size for such comparisons was assumed to be 80% of the effect size for the comparison between fasinumab 1 mg Q4W group and the placebo group. Under these assumptions, enrollment of 600 patients in the fasinumab 1 mg Q8W group and 200 patients from the placebo group would have provided 97% power to detect an effect size of 0.368 (=0.46\*80%) in the WOMAC pain and physical function subscale scores at week 16 and 93% power at week 52. This sample size would have provided 84% power to detect an

effect size of 0.288 (=0.36\*80%) in PGA at week 16, and 75% power at week 52 for the FAS.

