- H1,16: There is no treatment difference between fasinumab 1 mg Q4W and naproxen in the proportion of patients with ≥30% improvement in the WOMAC pain subscale scores at week 16 versus there is treatment difference in proportion of patients with ≥30% improvement in WOMAC pain at week 16
- H2,1: There is no treatment difference between fasinumab 1 mg Q8W and placebo in WOMAC pain or physical function subscale scores at week 16 versus there is treatment difference in WOMAC pain and physical function subscale scores at week 16
- H2,2: There is no treatment difference between fasinumab 1 mg Q8W and placebo in Patient Global Assessment score at week 16 versus there is treatment difference in Patient Global Assessment score at week 16
- $H_{2,3}$ : There is no treatment difference between fasinumab 1 mg Q8W and placebo in the proportion of patients with  $\geq 30\%$  improvement in the WOMAC pain subscale scores at week 16 versus there is treatment difference in proportion of patients with  $\geq 30\%$  improvement in WOMAC pain at week 16

- H2,4: There is no treatment difference between fasinumab 1 mg Q8W and naproxen in the WOMAC pain subscale scores at week 16 versus there is treatment difference in WOMAC pain subscale scores at week 16
- H2,5: There is no treatment difference between fasinumab 1 mg Q8W and naproxen in the WOMAC physical function subscale scores at week 16 versus there is treatment difference in WOMAC physical function subscale scores at week 16
- H2,6: There is no treatment difference between fasinumab 1 mg Q8W and placebo in WOMAC pain subscale scores at week 44 versus there is treatment difference in WOMAC pain subscale scores at week 44
- H2,7: There is no treatment difference between fasinumab 1 mg Q8W and placebo in WOMAC physical function subscale scores at week 44 versus there is treatment difference in WOMAC physical function subscale scores at week 44
- H2,8: There is no treatment difference between fasinumab 1 mg Q8W and placebo in Patient Global Assessment score at week 44 versus there is treatment difference in Patient Global Assessment score at week 44
- H2,9: There is no treatment difference between fasinumab 1 mg Q8W and naproxen in Patient Global Assessment score at week 16 versus there is treatment difference in Patient Global Assessment score at week 16

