# **10.2.** Justification of FAS and mFAS Sample Sizes

In this study, approximately 2560 patients were to be randomized to fasinumab 1 mg SC Q4W (840), fasinumab 1 mg SC Q8W (600), naproxen (840), or placebo (280) (see Section 5.1.3). This sample size was expected to provide adequate power for the comparisons between fasinumab and naproxen at week 16 for the WOMAC pain and physical function scores and the PGA score and provide long term data for safety assessment.

The sample size for the full analysis set (FAS) population was based on results of the WOMAC pain and physical function subscale scores and the PGA from the R475-PN-1227 study. The calculation of sample size assumed a 2-sided alpha level of 0.025 and a 15% dropout rate up to week 16 and a 30% dropout rate up to week 52. Enrollment of 840 patients in the fasinumab 1 mg Q4W group and 280 patients in the placebo group would have provided at least 99% power to detect an effect size of 0.46 in the WOMAC pain and physical function subscale scores (ie, an absolute treatment difference of 1.1 between fasinumab and placebo and a standard deviation [SD] of 2.4 at week 16 and 52 for the FAS). This sample size would have provided 99% power to detect an effect size of 0.36 in PGA for an absolute treatment difference of 0.4 with an SD of 1.1 at week 16, and 98% power at week 52 for the FAS.

For the fasinumab 1 mg Q8W group, the 600 patients in the FAS population were to be compared to approximately 200 patients in the placebo group who were enrolled after amendment 5 global was implemented. For such comparisons, 2-sided alpha level of 0.025 and a 15% dropout rate up to week 16 and a 30% dropout rate up to week 52 were assumed. Additionally, the effect size for such comparisons was assumed to be 80% of the effect size for the comparison between fasinumab 1 mg Q4W group and the placebo group. Under these assumptions, enrollment of 600 patients in the fasinumab 1 mg Q8W group and 200 patients from the placebo group would have provided 97% power to detect an effect size of 0.368 (=0.46\*80%) in the WOMAC pain and physical function subscale scores at week 16 and 93% power at week 52. This sample size would have provided 84% power to detect an effect size of 0.288 (=0.36\*80%) in PGA at week 16, and 75% power at week 52 for the FAS.

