The sample size calculation was also based on previously reported results of the WOMAC pain subscale and physical function subscale and the PGA for naproxen (Ekman 2014) (Schnitzer 2015). Assuming a 2-sided alpha level of 0.025 and a 15% dropout rate up to week 16 and a 30% dropout rate up to week 52, an enrollment of 840 patients in the fasinumab 1 mg Q4W group and the naproxen group would have provided at least 97% power to detect an effect size of 0.22 in the WOMAC pain subscale (ie, an absolute treatment difference of 0.51 with an SD of 2.3) at week 16, and 92% power at week 52 for FAS. This sample size would have provided 98% power to detect an effect size of 0.24 in WOMAC physical function subscale (ie, absolute treatment difference of 0.50 with an SD of 2.1) at week 16, and 96% power at week 52 for FAS. This sample size would have provided 87% power to detect an effect size of 0.18 in PGA at week 16 between fasinumab 1 mg Q4W and naproxen for the FAS.

Due to regional irregularities noted in a parallel phase 3 study that became fully apparent only after unblinding that study, and the concern that the same irregularities would be present in data from similar sites in this study, the population for the primary and secondary efficacy analyses was changed in Protocol Amendment 8 to be based on a modified full analysis set (mFAS) that excludes the randomization stratum for that region. Based on the assumptions above, it is estimated that this mFAS will provide:

 99.9% power to detect a significant difference between the 1 mg Q4W group and the placebo group in the WOMAC pain and physical function subscales at an alpha level of 0.05

- 42% and 46% power to detect a significant difference between the 1 mg Q8W group and the placebo group in WOMAC pain and physical function subscales, respectively, at an alpha level of 0.01
- 99.9% power to detect a significant difference between the 1 mg Q4W group and the naproxen group in the WOMAC pain and physical function subscales at an alpha level of 0.04

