## 2.2. Sample Size and Power Considerations

In this study, approximately 2560 patients were planned to be randomized to fasinumab 1 mg SC Q4W (840), fasinumab 1 mg SC Q8W (600), naproxen (840), or placebo (280) (see Section 5.1.3 of the protocol). This sample size was expected to provide adequate power for the comparisons between fasinumab and naproxen at week 16 for the WOMAC pain and physical function scores and the Patient Global Assessment - Osteoarthritis (PGA-OA) score and provide long term data for safety assessment.

The sample size was based on results of the WOMAC pain and physical function subscale scores and the PGA from the R475-PN-1227 study. The calculation of sample size assumed a 2-sided alpha level of 0.025 and a 15% dropout rate up to week 16 and a 30% dropout rate up to week 52. Enrollment of 840 patients in the fasinumab 1 mg Q4W group and 280 patients in the placebo group would have provided at least 99% power to detect an effect size of 0.46 in the WOMAC pain and physical function subscale scores (i.e., an absolute treatment difference of 1.1 between fasinumab and placebo and a standard deviation [SD] of 2.4 at week 16 and 52 for the full analysis set [FAS]). This sample size would have provided 99 % power to detect an effect size of 0.36 in PGA for an absolute treatment difference of 0.4 with a SD of 1.1 at week 16, and 98% power at week 52 for the FAS.

For the fasinumab 1 mg Q8W group, the 600 patients would have been compared to the approximately 200 patients in the placebo group who were enrolled after Protocol R475-OA-1611 Amendment 5 Global was implemented. For such comparisons, 2-sided alpha level of 0.025 and a 15% dropout rate up to week 16 and a 30% dropout rate up to week 52 were assumed. Additionally, the effect size for such comparisons were assumed to be 80% of the effect size for the comparison between fasinumab 1 mg Q4W group and the placebo group. Under these assumptions, enrollment of 600 patients in the fasinumab 1 mg Q8W group and 200 patients from the placebo group would have provided 97% power to detect an effect size of 0.368 ( $=0.46*80%$ ) in the WOMAC pain and physical function subscale scores at week 16 and 93% power at week 52. This sample size would have provided 84% power to detect an effect size of 0.288 ( $=0.36*80%$ ) in PGA at week 16, and 75% power at week 52 for the full analysis set (FAS).

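### The adequate-power statement for fasinumab versus naproxen is backed by a calculation for 1 mg Q4W only; for 1 mg Q8W the plan's own assumptions, chained together, imply power of about 30% to 55% at alpha 0.025

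*Protocol*

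**What the plan says.** The Synopsis, under the FAS and mFAS sample size justification, states that the planned size was "expected to provide adequate power for the comparisons between fasinumab doses and naproxen at week 16" for the two WOMAC subscales and PGA. Two doses remain in the efficacy comparisons, 1 mg Q4W and 1 mg Q8W. Protocol 10.2 words it as "expected to provide adequate power for the comparisons between fasinumab and naproxen at week 16", and SAP 2.2 likewise begins "This sample size was expected to provide adequate power for the comparisons between fasinumab". Neither limits the statement to a dose.

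The supporting naproxen calculations in all three places are for Q4W: 840 per arm, "Assuming a 2-sided alpha level of 0.025 and a 15% dropout rate up to week 16", and for pain "an absolute treatment difference of 0.51 with an SD of 2.3". Stated week 16 power is 97% (pain), 98% (function) and 87% (PGA). The mFAS naproxen figure is also for Q4W only.

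For Q8W, power is given against placebo only. There the "effect size for such comparisons was assumed to be 80% of the effect size for the comparison between fasinumab 1 mg Q4W group" and placebo. Q8W versus naproxen is nevertheless tested: H2,4 reads "There is no treatment difference between fasinumab 1 mg Q8W and naproxen in the WOMAC pain subscale scores at week 16", H2,5 covers function and H2,9 covers PGA. Protocol 10.3.1 and 10.3.2 restrict Q8W comparisons to concurrently randomized controls.

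**The concern.** A general statement of adequate power covers comparisons for which no effect size and no power is given. Those comparisons sit in the alpha-controlled family and concern exactly the three endpoints the statement names.

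The missing case also looks much weaker than the one calculated. Q8W is assumed to be less effective than Q4W, and the Q4W advantage over naproxen is already small, so a modest loss of effect removes a large share of it. The Q8W comparison also loses the control patients randomized before Amendment 5. If the statement is taken at face value, a non-significant H2,4, H2,5 or H2,9 could be read as evidence that Q8W is no better than naproxen, when the design may have had limited ability to show the difference its assumptions imply.

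**Working it through.** **Inputs**
- Q4W versus placebo, WOMAC: "an absolute treatment difference of 1.1 between fasinumab and placebo and a standard deviation [SD] of 2.4", effect size 0.46; PGA difference 0.4, SD 1.1, effect size 0.36 (Protocol 10.2).
- Q8W effect: 80% of Q4W's, stated for the placebo comparison (Protocol 10.2).
- Q4W versus naproxen: pain 0.51, SD 2.3 (effect size 0.22); function 0.50, SD 2.1 (0.24); PGA effect size 0.18 (Protocol 10.2).
- Randomized under Amendment 5: 600 Q8W and 600 naproxen (Protocol 5.1.3). With 15% dropout, 600 × 0.85 = 510 evaluable per arm.

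**Formula.** Two-sample normal approximation: power = Φ(ES × √(n1·n2/(n1+n2)) − z), with z = 2.241 for two-sided alpha 0.025.

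**Reproducing the plan's figures**
- Q4W versus naproxen, 840 × 0.85 = 714 per arm, √357 = 18.89. Pain: 0.22 × 18.89 − 2.241 = 1.92, giving 97.2% (stated 97%). Function: 98.9% (stated 98%). PGA: 87.7% (stated 87%).
- Q8W versus placebo, 510 versus 170, √127.5 = 11.29. WOMAC at 0.368: 97.2% (stated 97%). PGA at 0.288: 84.4% (stated 84%).

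The method therefore matches the plan's.

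**Implied Q8W-naproxen effect (an assumption; the documents give none).** (Q8W − naproxen) = (Q4W − naproxen) − 0.20 × (Q4W − placebo). The placebo and naproxen comparisons use different SDs, so the result depends on whether raw points or effect sizes are subtracted.
- Pain, raw: 0.51 − 0.22 = 0.29; 0.29/2.3 = 0.126. Effect sizes: 0.22 − 0.092 = 0.128.
- Function, raw: 0.50 − 0.22 = 0.28; 0.28/2.1 = 0.133. Effect sizes: 0.24 − 0.092 = 0.148.
- PGA, effect sizes: 0.18 − 0.072 = 0.108. No naproxen SD is stated for PGA; borrowing SD 1.1 gives (0.198 − 0.08)/1.1 = 0.107 and about the same power.

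**Power, 510 per arm (√255 = 15.97)**

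| Assumed effect | ES | alpha 0.05 | alpha 0.025 | alpha 0.01 |
|---|---|---|---|---|
| Pain, raw points | 0.126 | 52.1% | 41.0% | 28.7% |
| Pain, effect sizes | 0.128 | 53.3% | 42.2% | 29.7% |
| Function, raw points | 0.133 | 56.7% | 45.5% | 32.8% |
| Function, effect sizes | 0.148 | 65.7% | 54.9% | 41.6% |
| PGA, effect sizes | 0.108 | 40.7% | 30.3% | 19.7% |
| Pain, 80% × 0.22 | 0.176 | 80.2% | 71.5% | 59.3% |
| Function, 80% × 0.24 | 0.192 | 86.6% | 79.5% | 68.8% |
| PGA, 80% × 0.18 | 0.144 | 63.3% | 52.3% | 39.1% |

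The last three rows apply 80% directly to the Q4W-naproxen effect size, a more lenient reading that the documents do not state either.

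**Other variants at alpha 0.025, raw-point effects for WOMAC**
- SD 2.4 for both WOMAC subscales: 38% (pain), 35% (function).
- No dropout, 600 per arm: 48% / 53% / 36% (pain / function / PGA).
- Adding the naproxen patients randomized before Amendment 5, contrary to the plan: 47% / 52% / 35%.
- Giving Q8W the whole Q4W advantage over naproxen, contrary to the 80% assumption: 90% / 94% / 74%.

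**The case against.** The plural, doses, appears only in the Synopsis. Protocol 10.2 and SAP 2.2 say fasinumab, and the figures that follow name Q4W, so a careful reader can see which dose was powered. Protocol 3.2.2 justifies the Q8W arm by exposure, replication of its efficacy profile and the search for a minimally efficacious dose, not by superiority to naproxen. The plan also discloses 42% and 46% power for Q8W versus placebo in the mFAS, so few readers would assume Q8W versus naproxen was well powered. Confidence intervals are planned. All of this stands and lowers the stakes, but it does not supply a calculation for the comparison that the sentence covers.

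A reader might infer more than the documents support:
- **That the documents fix Q8W-naproxen power at 30-46%.** They do not. The 80% ratio is stated only against placebo. The implied effect joins a fasinumab trial with published naproxen results that have different SDs, and subtracting effect sizes puts function at 55%.
- **That alpha 0.01 applies to these tests.** The power section attaches 0.01 to Q8W versus placebo only. The testing graph (SAP Figure 2) is not shown in the text available, alpha is reallocated after rejections, and SAP 2.2 says the levels used differ from the sample size assumptions.
- **That mFAS power can be derived from these figures.** For the same effect, SD and alpha, a subset cannot have more power than the FAS it comes from, but mFAS numbers are not given. The stated 99.9% for Q4W versus naproxen at alpha 0.04 exceeds what 714 per arm gives under the FAS effect sizes (98.2% pain, 99.3% function), so the FAS inputs do not carry over simply.
- **That a stated power figure is wrong.** The stated FAS figures reproduce to within 2 percentage points.

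**Conclusion.** The point holds as an unsupported statement and an omitted figure. No calculation backs adequate power for Q8W versus naproxen.

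Under the implied effect, with 510 evaluable concurrent patients per arm and alpha 0.025, power is about 41-42% for pain, 46-55% for function and 30% for PGA. At alpha 0.05 it is about 52-53%, 57-66% and 41%; at 0.01, about 29-30%, 33-42% and 20%. These rest on carrying the 80% placebo ratio over to the naproxen comparison and on the planned FAS numbers.

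The lenient reading softens the picture for WOMAC: about 72% and 80% at alpha 0.025, and 80% and 87% if the full 0.05 were available. PGA stays low at 52% and 63%. At the planning alpha of 0.025, PGA falls below the plan's own lowest week 16 naproxen figure (87%) on every reading tried, including 74% with the full Q4W advantage. So the statement cannot stand for both doses on all three endpoints, although how far short pain and function fall depends on the reading.

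**What to change.** - In the Synopsis, Protocol 10.2 and SAP 2.2, limit the adequate-power statement to fasinumab 1 mg Q4W versus naproxen.
- In the same places, state that Q8W versus naproxen was not adequately powered. Give its power for pain, function and PGA as a range, with the assumed difference, the SD, the alpha that the testing graph can deliver to H2,4, H2,5 and H2,9, and the actual concurrent mFAS numbers per arm.
- Label the Q8W-naproxen effect as an assumption and say how it was obtained.

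The cost is a less favourable statement and a short calculation. No patients, analysis or alpha allocation change.

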#### Statistical Methods

Baseline demographic disease characteristics, including medical history and exposure to study drug, will be summarized by treatment group using descriptive statistics. Continuous variables will be summarized with mean, median, standard deviation, minimum, and maximum. For categorical or ordinal data, frequencies and percentages will be displayed for each category.

The primary efficacy variables will be analyzed using multiple imputation approach with a mixed-effect model for repeated measure (MMRM) based on the mFAS with adjustment for missing data due to lack of efficacy, death or AEs assuming the WOMAC scores would on average return to baseline values. The imputed data for patients discontinued from the study treatment due to lack of efficacy, death or AEs will be centered at the mean baseline value. The missing data for patients who discontinued treatment due to other reasons will be imputed under missing-at-random assumption. Sensitivity analysis using tipping point approach with multiple imputation will be performed to assess the robustness of the results due to treatment discontinuation.

For analysis of continuous secondary endpoints at fixed timepoints (ie, week 16 and week 44), the analysis method will be the same as that used for the primary efficacy endpoints. For the analysis of secondary endpoints involving the averaging over several visits, analysis will be performed using a multiple imputation approach with an ANCOVA model based on the mFAS with adjustment for missing data performed in the same manner as was done for the primary endpoint. For analysis of secondary endpoints that are categorical variables, eg, proportions of patients with ≥30% improvement in the WOMAC pain subscale scores at week 16, the Cochran Mantel Haenszel approach will be used based on the mFAS, stratifying by the randomization strata.

For Year 2 analysis, the efficacy and patient-reported outcome (PRO) endpoints collected will be summarized descriptively.

The summary of safety results will be presented for Year 1, Year 2, and the combined treatment period of Year 1 and Year 2.

Safety data including TEAEs and treatment emergent adverse events of special interest, vital signs, physical exams, laboratory tests, electrocardiograms, and anti-drug antibody formation will be listed and summarized by treatment group.

# LIST OF ABBREVIATIONS AND DEFINITIONS OF TERMS

5-ASA 5-aminosalicylic acid

AA Adjudicated arthropathy

ACE Angiotensin-converting enzyme

ADA Anti-drug antibody

ADL Activities of daily living

AE Adverse event

AESI Adverse event of special interest

ALT Alanine aminotransferase
AST Aspartate aminotransferase
ARB Angiotensin receptor blocker

bpm Beats per minute
BUN Blood urea nitrogen
Cmax Maximal concentration
COVID-19 Coronavirus Disease 2019

CPK Creatine phosphokinase

CRF Case report form (electronic or paper)

CRO Contract research organization

Ctrough Trough concentrations

CTCAE Common Terminology Criteria for Adverse Events

DA Destructive arthropathy

DMC Data Monitoring Committee

EC Ethics Committee
ECG Electrocardiogram

EDC Electronic data capture

EQ-5D-5L EuroQoL 5 Dimensions 5 Level Questionnaire

ESR Erythrocyte sedimentation rate

FAS Full analysis set

FDA Food and Drug Administration
FSH Follicle-stimulating hormone

GCP Good Clinical Practice
GFR Glomerular filtration rate

GI Gastrointestinal
HbA1c Hemoglobin A1c

HCRU Healthcare Resource Utilization
hs-CRP High-sensitivity C-reactive protein

ICF Informed consent form

ICH International Council for Harmonisation

INR International normalized ratio
IRB Institutional Review Board

IVRS Interactive voice response system
IWRS Interactive web response system

JR Joint replacement
K-L Kellgren-Lawrence

IV Intravenous

LDH Lactate dehydrogenase mAb Monoclonal antibody

MedDRA Medical Dictionary for Regulatory Activities

mFAS Modified Full Analysis Set

MMRM Mixed-effect Model for Repeated Measures

MRI Magnetic Resonance Imaging

NAb Neutralizing antibody
NGF Nerve growth factor
NRS Numeric Rating Scale

NSAID Non-steroidal anti-inflammatory drug

OA Osteoarthritis

OMERACT- Osteoarthritis Research Society International Standing Committee for Clinical OARSI Trials Response Criteria Initiative and The Outcome Measure in Rheumatology

PCSV Potentially clinically significant value

PGA Patient Global Assessment

PK Pharmacokinetic
PPS Per protocol set

prn Pro re nata

PRO Patient-reported outcome

PT Preferred term

QRS Complex of Q, R, and S waves on an electrocardiogram

Q4W Every 4 weeks Q8W Every 8 weeks RBC Red blood cell

Regeneron Pharmaceuticals, Inc.

SAE Serious adverse event SAF Safety analysis set

SAP Statistical analysis plan

SAS Statistical Analysis Software

SC Subcutaneous

SD Standard deviation

SF-36 36-item Short Form Survey

SOC System organ class

SUSAR Suspected unexpected serious adverse reaction

TBL Total bilirubin

TEAE Treatment-emergent adverse event

TJR Total joint replacement
TrkA Tyrosine kinase type 1

TSQM Treatment Satisfaction Questionnaire for Medication

ULN Upper limit of normal

USMS Urgent Safety Measure Set

WBC White blood cell

WOCBP Woman of child-bearing potential

WOMAC Western Ontario and McMaster Universities Osteoarthritis Index

WPAI-OA Work Productivity and Activity Impairment-Osteoarthritis

